1.2. FLUORESCENCE GUIDED SURGERY

The most promising technology to reduce the positive margin rate in sarcoma surgery is fluorescence guided surgery (FGS). FGS is an established method, which involves the administration of fluorescent dye followed by visualisation of the fluorescence intensity with a near-infrared (NIR) camera intraoperatively.

Indocyanine green (ICG) is a widely used fluorescent dye, which has been used for decades to assess cardiac output¹⁵ and hepatic function.¹⁶ ICG is approved by the European Medicines Agency (EMA). It is considered safe and has rarely been linked to adverse events in other settings.^{17,18} More recently it has been used for tissue perfusion assessments intra-operatively in other surgical fields, allowing surgeons to more accurately identify healthy tissue from tissue that is diseased or poorly vascularised.^{19,20}

The most recent application of FGS using ICG is for tumour margin identification of solid cancers.²¹⁻²⁵ ICG is administered intravenously prior to the operation, allowing time for uptake of the dye into the tumour and clearance from the peritumoral tissue. The half-life of ICG in the circulation is short at approximately three minutes²⁶ but is long enough to allow for tumour uptake. The first reports of FGS using ICG for tumour margin identification are from liver cancer resection, demonstrating efficacy for tumour margin identification following administration of an intravenous ICG dose of 0.5mg/kg at least one day prior to surgery.²⁷ In 2019 surgeons and researchers at the North of England Bone and Soft Tissue Tumour Service, conducted and published the world's first case series demonstrating that most intermediate- to high-grade sarcomas fluoresce, and in some procedures this fluorescence was used to guide surgery.²⁸ During the same time period, an early phase trial assessing the feasibility of FGS using ICG for tumour margin identification in all types of paediatric solid cancers was conducted at St Jude Children's Research Hospital in Tennessee USA.²⁹ The methodology for this trial was intravenous injection of ICG at 1.5mg/kg one day prior to surgery. The results demonstrated that from the 65 cases recruited, 29 were sarcomas, of which 27 demonstrated fluorescence with high sensitivity (88%) for tumour identification, although specificity was lower (77%). This trial complements our case series findings that tumour margin identification using FGS could have the potential to greatly improve patient outcomes but requires further investigation. It also validates our proposed methodology of ICG dosage, timing, and route of administration. There were no adverse events related to the ICG administration indicating it is a safe and valid technique.^{28,29}

1.3. Indocyanine Green

The Newcastle Sarcoma Research Group has undertaken extensive preclinical and histopathological studies to investigate the mechanisms of uptake of ICG in sarcoma cell lines and patient tumour samples.³⁰ We have demonstrated that a key mechanism of ICG cellular uptake is clathrin mediated endocytosis (Figure 2). Figure 2 illustrates how ICG uptake is diminished following treatment with the inhibitor. We have also demonstrated that cellular proliferation rate correlates with fluorescence intensity, indicating that cancer cells with the shortest doubling time take up more ICG. Furthermore, we have been successful at visualising ICG at the cellular level at the margins of sarcoma specimens (Figure 3). There are two factors involved in ICG uptake in sarcoma, 1) is the enhanced permeability and retention effect in the tumour, which allows the ICG to accumulate in areas of haemorrhage and necrosis within in the tumour and 2) is the sarcoma cell uptake via the endocytosis mechanism. This has explained our case series finding that higher grade sarcomas take up more ICG²⁸ because of the combination of increased cellular activity and the presence of areas of haemorrhage and necrosis in these tumours.

Figure 2. *In vitro* Fluorescence microscopy images of ICG uptake in HT1080 sarcoma cells with and without the presence of an inhibitor of clathrin mediated endocytosis. The image on the right demonstrates that ICG uptake is diminished following treatment with the inhibitor.

Figure 3. Histopathology slide imaged using an NIR microscope from an osteosarcoma patient who received ICG for FGS. ICG accumulation is demonstrated in areas of haemorrhage and there is uptake into osteosarcoma cells. A white dashed line has been marked, which demonstrates the margin.

2. RATIONALE

During evidence synthesis for this trial, we found some variability in reported negative versus positive margins rates from centres around the UK. Furthermore, the definitions of margin status can be misleading. Statements in the literature regarding 'planned positive margins' are not helpful. Expert sarcoma surgeons understand the concept that a 'planned positive margin' is usually acceptable in terms of not undertaking a further resection because the margin is at a critical structure such as a major nerve or blood vessel. However, a 'planned positive margin' is not always positive- it may be negative, albeit close to the tumour. Therefore, for the purposes of this trial the terminology for margins post-surgery based on the pathology report of the resected specimen will be as follows:

- Negative margin: with the closest distance to the tumour measured in millimetres
- Unexpected positive macroscopic margin
- Unexpected positive microscopic margin
- Acceptable positive macroscopic margin
- Acceptable positive microscopic margin

In November 2020, the National Cancer Research Institute Sarcoma Research Group (UK) reached a consensus that trials in surgery are a priority to assess new technologies that may improve surgical performance.³¹ To date there have been no randomised sarcoma trials with a surgical intervention. Recently published case series data suggested that the use of FGS using ICG for high grade sarcoma resection may reduce the UPM rate.³² As such, undertaking this randomised control trial of FGS in sarcoma is well-timed. This trial will be exclusive to sarcoma patients, but inclusive of all ages and subtypes except low grade sarcomas because they do not fluoresce. Delivery of this trial will provide the sarcoma community, nationally and internationally, with crucial insights into performing more effective surgery, the opportunity to develop improvements to the current standard surgical and histopathological techniques, answers to questions on functional outcomes and the optimal timing of adjuvant therapies. With UPMs clearly linked to inferior oncological outcomes in the short term (e.g., decreased time to local recurrence) and longer term (e.g., poorer overall survival), this randomised surgical trial represents an important step towards improving these outcomes for sarcoma patients.

2.1. Risk Assessment

The NCTU Risk Assessment Categorisation Tool was completed signed off by the relevant authority. The Newcastle University Data Protection Impact Assessment was completed and signed off by the relevant authority.

The trial is categorised as low risk.

3. OBJECTIVES AND OUTCOME MEASURES

3.1. Objectives

3.1.1. Primary Objectives

To determine whether there is a reduction in the unexpected positive margin rate (UPM) in patients receiving fluorescence-guided surgery (FGS) using indocyanine green (ICG) compared to standard of care (SoC).

3.1.2. Secondary Objective(s)

To determine the effect of FGS using ICG compared to the SoC over a 12-month period on the following areas:

- o Complications
- Length of index operation
- Length of inpatient stay

- Perceived impact of the intervention on surgical decision and change in surgeon preference throughout the trial
- Local recurrence
- Regional/distal recurrence
- Rates of adjuvant and neo-adjuvant therapies.
- Overall survival
- Quality of life (QoL)
- Recovery following resection

3.1.3. Exploratory Objectives

There are two exploratory objectives: 1) to determine the role of ICG in the pathological margin assessment of resected sarcoma specimens whilst improving understanding of the cellular mechanisms of FGS using ICG and 2) to develop fluorescence mapping algorithms to improve interpretation of fluorescence.

3.2. Outcome Measures

3.2.1. Primary outcome measure

The primary outcome measure is the UPM rate. The margin status of each tumour will be taken from the pathology report for each patient enrolled in the trial. This will be recorded at six months postsurgery and will be classified according to the R classification system.⁶ Positive margins will be classified as the visualisation of tumour cells at the inked margin and will then be classified as acceptable or unexpected. The UPM rate for each arm will be defined by calculating the percentage of patients in that arm with a UPM on histopathological assessment of the resection specimen. If a negative margin is recorded, the size of the closest margin should be recorded in millimetres.

In this trial, the estimand aims to answer the research question: does fluorescence-guided surgery using indocyanine green (ICG) reduce the UPM compared to the standard of care (SoC)?

Estimand attribute	Description
Treatment	Fluorescence guided surgery (FGS) using indocyanine green (ICG) compared to standard of care (SoC) surgery
Population	Patients of all ages with a histologically confirmed diagnosis of intermediate to high grade bone or soft tissue sarcoma suitable for curative resection
Variable (outcome)	Unexpected positive margin (UPM)
Intercurrent events	There are no anticipated intercurrent events with respect to the observation of the primary outcome
Population-level summary measure	The difference in the UPM rates between the FGS group and SoC group

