Population	intermediate to high-grade bone or	soft tissue sarcoma suitable for		
	curative resection.			
Planned Sample Size	Total n=500 (FGS with ICG n=250, S	tandard Care n=250)		
Planned Number of	Up to 20			
Sites				
Intervention Duration	12–24-hour time period between t	ne administration of intravenous		
	(IV) ICG and the start of the resection.			
Follow Up Duration	Patients will be followed up for 12 months following the procedure,			
	with the option of an additional time point at 5 years if further funding			
	is secured.			
Planned Trial Period	58 months (7 months setup, 30 mo	nths of recruitment, 3 months		
	surgical delay, 12 months follow up	, 6 months final		
	report/dissemination)			
	Objectives Outcome Measures			
Primary	To determine whether FGS using	The UPM rate, defined as the		
	ICG reduces the UPM rate	percentage of patients with an		
	compared to the current standard	unexpected positive margin, will		
	of care (SoC).	be compared between the two		
	treatment arms.			
Secondary	Complications	Rates of intra- and postoperative		
	complications as recorded in the			
	clinical notes.			
	Length of index operation Difference in length of operation			
	in minutes.			

TRIAL SUMMARY

	Length of inpatient stay	Difference in length of inpatient stay in days.			
	Perceived impact of intervention in surgical decision making	The percentage of operations in which the surgeon stated FGS changed their planned resection.			
	Local recurrence (LR) rate	The difference in rate of local recurrence at 12 months.			
	Regional/distal recurrence rate	The difference in rate of regional/distal recurrence at 12 months.			
	Overall survival (OS) rate	The difference in rate of overall survival at 12 months.			
	Identify rates of adjuvant and neo-adjuvant therapies	Rates of adjuvant and neo- adjuvant therapies as per clinical notes.			
	Quality of life (QoL) measurements	The difference in scores on EQ- 5D-5L/EQ-5D-Y.			
	Recovery following resection	The difference in scores on the Toronto extremity salvage score (TESS)/ Paediatric Toronto extremity salvage score (pTESS)			
Exploratory Objectives	To determine the role of ICG in the pathological margin assessment of resected sarcoma specimens	Fluorescence microscopy to assess extracellular and cellular ICG spatial orientation in tumour tissue versus surrounding normal tissues			

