3.3. Outcomes

3.3.1. Primary Outcome

The pathology report of the resected tumour will provide a margin status. The percentage of patients with unexpected positive margins will be calculated for each group to give the unexpected positive margin rate. This will then be compared between the two groups as described in section 10.2.1.

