10.2. Statistical Analyses

10.2.1. Analysis of the Primary Outcome Measure

Once margin data has been collected for 250 patients, an interim analysis will be conducted using a Barnard test to calculate a one-sided p-value, with non-binding stopping rules for both overwhelming efficacy and futility with regards to the primary outcome. The final analysis will then occur either after the interim analysis (if the trial stops) with all participants that have been recruited by the time the interim decision is made, or after the full target enrolment is reached (if the trial does not stop). All participants will be followed up for all outcomes, with final data cleaning and database lock occurring after that time. The primary analysis will be based on the Intention-to-treat (ITT) population with all participants included in the group they were randomised to. We do not anticipate a significant number of noncompliance and cross-over issues. If we encounter any protocol deviations or violations related to the treatment allocation, we will also define a perprotocol (PP) population for secondary analyses, in which participants for whom the allocated strategy was not followed will be excluded. All analyses will be described in a Statistical Analysis Plan (SAP) that will be finalised prior to trial statisticians receiving any unblinded data. For the analysis of the primary outcome, UPM rate, we will use a logistic regression that adjusts for key covariates including stratification factors used in the randomisation. A Wald test and a 95% confidence interval will be extracted from this model. A two-sided p-value will be found from the Wald test, although ICG will only be recommended as efficacious if the one-sided p-value for superiority of ICG is <0.0227.

Secondary analyses for the primary outcome will include the per-protocol population and a method that can account for the learning effect such as the hierarchical model approach proposed by Cook

et al ³⁶. Since the UPM rate is measured quickly after randomisation, we anticipate very low missing outcome data. Nevertheless, if this rate is higher than 5%, we will investigate applying a suitable missing at random (MAR) approach such as multiple imputation.

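### The estimand is a difference in UPM rates, but section 10.2.1 plans no adjusted estimate or confidence interval on that scale

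*Protocol*

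**What the plan says.** Protocol section 3.2.1 contains an estimand table. Its summary-measure row reads "The difference in the UPM rates between the FGS group and SoC group". The same section defines the quantity being compared: "The UPM rate for each arm will be defined by calculating the percentage of patients in that arm with a UPM". This is an absolute, marginal scale: a percentage in each arm, and the difference between the two.

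Section 3.3.1 says: "The percentage of patients with unexpected positive margins will be calculated for each group to give the unexpected positive margin rate". It then hands the comparison on: "This will then be compared between the two groups as described in section 10.2.1".

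Section 10.2.1 names one final analysis of the primary outcome: "we will use a logistic regression that adjusts for key covariates including stratification factors used in the randomisation". What is taken from it is stated as follows: "A Wald test and a 95% confidence interval will be extracted from this model". The effect scale of that interval is not named. The decision rule is a p-value threshold: "ICG will only be recommended as efficacious if the one-sided p-value for superiority of ICG is <0.0227".

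The other analyses of the primary outcome in section 10.2.1 (per-protocol, learning effect, interim Barnard test) are not said to yield a rate difference with an interval. Nowhere does the protocol mention standardisation, predicted risks or a risk difference from the model, and nowhere does it mention an odds ratio.

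**The concern.** An estimand's summary measure should be what the primary analysis estimates. Here the chain runs from section 3.2.1 (difference in rates) through section 3.3.1 (percentages, compared as in 10.2.1) to section 10.2.1, where it arrives at a model whose treatment coefficient is a log odds ratio conditional on the covariates. No step brings the result back to the difference in rates.

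If section 10.2.1 is followed literally, the headline estimate and interval describe a different quantity from the one the protocol says it is estimating. The trial was planned on two percentages, and the absolute reduction in unexpected positive margins is what readers will look for. A crude difference could be reported beside the model, but it would have no planned interval. It would also differ in both scale and adjustment from the analysis that carries the decision.

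**Working it through.** The plan states no effect-measure figure to reproduce. The check therefore takes its planning rates as inputs, asks whether the two scales can stand in for each other, and then asks whether the planned model can deliver the stated measure.

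**Inputs (Protocol).** Planning rates 13.8% (SoC) and 5.1% (FGS), section 10.3. UPM rates of 9% and 16.3% from other sources, section 10.3. Range of reported positive margin rates 8% to 29.9%, sections 1.1 and 10.3. 250 patients per arm, trial summary.

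**Step 1. Both measures at the planning rates.**
- Risk difference = 0.051 − 0.138 = −0.087, that is −8.7 points.
- Odds ratio = (0.051/0.949) / (0.138/0.862) = 0.05374/0.16009 = 0.336.
- Risk ratio = 0.051/0.138 = 0.37.

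**Step 2. Approximate 95% intervals at 250 per arm, unadjusted.**
- Difference: SE = √(0.138×0.862/250 + 0.051×0.949/250) = 0.0259. Interval −8.7 ± 1.96×2.59, that is −13.8 to −3.6 points.
- Odds ratio: SE of the log = √(1/(250×0.138×0.862) + 1/(250×0.051×0.949)) = 0.341. Interval 0.17 to 0.65.

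**Step 3. What one odds ratio means at different control rates.** With control rate c, the FGS odds are o = 0.336 × c/(1 − c), the FGS rate is o/(1 + o), and the difference is o/(1 + o) − c. The unrounded odds ratio, 0.3357, is used.

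| Control rate | FGS rate | Difference (points) |
|---|---|---|
| 8% | 2.8% | −5.2 |
| 9% | 3.2% | −5.8 |
| 13.8% | 5.1% | −8.7 |
| 16.3% | 6.1% | −10.2 |
| 29.9% | 12.5% | −17.4 |

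The end rows use the protocol's quoted range for positive margins generally. Across the UPM rates that it cites (9%, 13.8%, 16.3%) the same odds ratio runs from 5.8 to 10.2 points. An odds ratio and its interval therefore do not give the stated summary measure without a control rate and a further step.

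**Step 4. Conditional and marginal odds ratios.** Assume two equal strata with control risks 5% and 22.6% (mean 13.8%) and a common odds ratio that brings the FGS mean to 5.1%. The conditional odds ratio is then 0.320 against 0.336 marginally, with the difference still −8.7 points. The effect is small, but it confirms that the model coefficient is not a re-expression of the difference.

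**Step 5. Whether the planned model can give the stated measure.** Under the Step 4 assumptions, with 250 per arm and 2,000 simulated trials, each adjusted logistic fit was followed by standardisation: the mean predicted risk with everyone set to FGS, minus the mean with everyone set to SoC. The mean difference was −8.8 points (SD 2.5). The crude difference averaged −8.8 (SD 2.6), and the true value was −8.7. The planned model recovers the estimand once this step is specified, with no loss of precision.

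**The case against.** **The rate difference is already planned.** Section 3.3.1 has each arm's percentage calculated, and in a 1:1 randomised trial the crude difference is a valid point estimate. This stands. A reader might infer that the estimand is never estimated at all, and the protocol does not support that. What is missing is an interval and an adjusted estimate on that scale.

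**The protocol never commits to an odds ratio.** This is also true. Section 10.2.1 names no scale, and a risk difference with a Wald interval can be derived from a logistic model. But a test and interval extracted from such a model are, by default, those of the treatment coefficient. Nothing in the text points to another reading.

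**The post-estimation step belongs in the SAP.** The SAP was not available for this review and may contain the step. However, the protocol itself fixes the summary measure, the model, the test and the source of the interval. The point is that two stated items do not connect, and a SAP that follows section 10.2.1 as written would carry the gap forward.

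**Adjustment as a larger problem.** A reader might infer that adjusting for up to 20 centres, subtype and expected margin will move the odds ratio materially through non-collapsibility. The size does not bear this out. With an assumed normal centre effect of SD 0.5 on the logit scale, the odds ratio moves only from 0.336 to 0.328. With 480 patients, 20 fixed centre effects and no true covariate effects at all, simulation still shifts the median log odds ratio by about 0.06. That shift is sparse-data bias, which is a different matter, and it rests on fixed centre terms that the protocol does not specify.

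**The decision is unaffected.** Largely so. No effect on one scale is no effect on the other, so the 0.0227 rule is barely touched.

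**Conclusion.** The point holds as a mismatch between sections 3.2.1 and 10.2.1. The stated estimand is a difference in rates, and the one final primary analysis yields, by default, a conditional log odds ratio with its interval. Only crude arm percentages are planned on the estimand's own scale.

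The consequence is confined to the reported effect and its interval. An odds ratio of 0.336 corresponds to anything from 5.2 to 17.4 points over the control rates that the protocol quotes, and to 8.7 points at its planning rate. The efficacy decision and the sample size do not change on this account. Nor is it a matter of the odds ratio grossly overstating the effect: 0.336 against a risk ratio of 0.37 is a modest gap, and it misleads only if the one is read as the other.

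The conclusion assumes the usual reading of section 10.2.1, that the interval is for the treatment coefficient. The conversion figures assume the planning odds ratio applies at every control rate. The standardisation result assumes the two-stratum set-up in Step 4. A correction is worthwhile because it concerns the trial's headline estimate and is nearly free.

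**What to change.** In section 10.2.1, keep the adjusted logistic regression and its Wald test for the decision rule. Add that the primary effect estimate is the marginal risk difference obtained from that model by standardisation: the average predicted UPM risk over all randomised patients under FGS, minus the same average under SoC. Its 95% confidence interval should come from the delta method or the bootstrap. Report the odds ratio as supportive, and carry the same wording into the SAP.

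If the odds ratio is in fact the intended measure, the alternative is to change the summary-measure row in section 3.2.1. Either way, the two sections should name the same quantity.

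The cost is a sentence or two in the protocol and one post-estimation step in the analysis code. It needs no new data, no change in sample size and, on the check above, no loss of precision.

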3.2.2. Secondary outcome measures

Complications

Complications may be split into both intraoperative and postoperative. Intraoperative complications could include:

- Blood loss requiring transfusion
- Inadvertent damage to nerves
- Inadvertent damage to tendons/ligaments
- Inadvertent damage to bony structures
- Myocardial infarction
- Stroke
- Other events determined by the PI to be a complication of the surgery

Postoperative complications could include:

- Wound infection
- Wound dehiscence
- Seroma
- Flap complications
- Deep vein thrombosis
- Pulmonary embolism
- Myocardial infarction
- Stroke
- Other events determined by the PI to be a complication of the surgery

Post operative complications will be graded by the PI at site using the Calvien Dindo Classifications of Surgical Complications ³³. The scale indicates the severity of the complication and the therapy needed to correct the complication. The scale consists of 7 grades of severity (I, II, IIIa, IIIb, IVa, IVb, V). See Section 16.4, Appendix 4 for a table of the Calvien Dindo Classifications of Surgical Complications.

Length of index operation

Length of index operation and length of inpatient stay will be measured in minutes and days, respectively.

Recurrence

Local/regional/distal recurrence is defined as the recurrence of sarcoma at the site of primary resection (local) or at a site other than that of the primary tumour, including distal metastasis. Investigations must be tailored to circumstances but where possible should include histological confirmation.

Therapies

Adjuvant and neo-adjuvant therapy rates will include radiation therapy and/or chemotherapy. The type and frequency of therapy will be recorded.

Survival Status

Overall survival (OS) is defined as death due to any cause. Where possible, the specific cause of death should be documented, allowing the calculation of disease specific survival.

Quality of Life

The QoL will be assessed using the EQ-5D-5L questionnaire that assesses quality of life in participants, evaluating the following five domains: mobility, self-care, usual activities, pain/discomfort and anxiety/depression.³⁴ The questionnaire is two pages in length and the '5L' refers to the five levels of severity on which responses to questions can be scored, ranging from 'no problems' to 'extreme problems'. This is used to produce a score to rate the participant's health related QoL. The EQ-5D-5L is not appropriate for participants younger than 16 years old because they may struggle to understand some of the questions. As such, the EQ-5D-Y questionnaire will be used for participants 8 to 15 years of age. This is based upon the same principles, but with the questions and answers phrased in a more child-friendly manner.³⁵ For participants 4 to 7 years old a proxy version of the EQ-5D-Y questionnaire will be completed by the participant's parent or main carer. For participants who may struggle to complete the EQ-5D-5L/EQ-5D-Y/proxy EQ-5D-Y on their own the questionnaire can be completed with the assistance of a research nurse in person or via telephone.

Recovery Following Resection

After undergoing surgical resection for sarcomas of the extremity, participants are often left with an element of functional impairment in the affected limb due to the extent of the resection required. There are separate questionnaires called the Toronto Extremity Salvage Score (TESS) for adult participants undergoing surgery on the upper and lower extremities. In these questionnaires participants are asked to rate their ability to perform several tasks, rating them from 'impossible' to 'not at all difficult', as well as overall rating of how disabled they feel they are. There is a paediatric version of the TESS (pTESS) which will be used for participants aged 7 to 17.9 years.

Surgical Impact and Decision Making

Immediately following the surgical procedure, a surgical case report form (eCRF/CRF) will be completed by the surgeon who performed the surgery. This eCRF/CRF will record if there was the potential for an acceptable close/positive margin due to the preservation of a critical structure, the length of the operation and any intra-operative complications. If the participant was randomised to the intervention arm, the eCRF/CRF will also record whether the surgeon felt this influenced their operative decision making.

